## **6. ASPECTS ETHICAL**

*to. General and particular rules for researchers.*

Researchers will strictly adhere to the provisions of this protocol and the good clinical practice, fully completing the data collection sheets.

Following the guidelines of the center, the study will be evaluated by the Ethics Committee of the Research with drugs from the San Carlos Clinical University Hospital. The current revision of the Helsinki declaration is the accepted basis for ethics in human research, and must be scrupulously followed and respected by all persons involved in said research.

*b. Informed consent.*

All patients will be informed, before starting the study, of the objectives, procedures and discomforts and risks of the study according to a specific information sheet. Informed consent information appears in the annex to this protocol.

*c. Benefit-risk assessment for research subjects:*

As it is a study that does not modify healthcare practice, it does not imply any added risk for patients. Ultrasound is a harmless technique, it requires the application of a gel water-soluble conductor, and can cause minor discomfort such as pain from the pressure exerted, redness or a small bruise.

*d. Security and confidentiality devices.*

The information disseminated and obtained by the implementation of this study is considered confidential and should be treated as such at all times.

Only the investigators will know the data (patient initials and history number) that can identify patients. Initials and patient record number will be separated of the rest of the notebook, and will not be entered in the study database. The patient will be identified by a numerical code in order to respect the confidentiality of the Personal data of patients, as established by Organic Law 3/2018, of December 5, of Protection of Personal Data and guarantee of digital rights. The collection and management of samples will follow the indications established in Law 14/2007, of July 3, on research biomedical.

In order to guarantee the confidentiality of the study data, they will only have access to the

The researcher and his team of collaborators, the Ethics Committee for Clinical Research, the relevant health authorities and the promoter's representatives.

The researcher agrees to collect, record and report the data in a reliable way and correct, responding to its updating and quality before the appropriate audits.

Patients will be identified by a number, both in the e-CRF and in the database. I know will guarantee the total confidentiality of the data, in particular the identity of the participants.

The data of the researchers and the study will be entered and processed in a proprietary file of PROMOTOR that will be responsible for the file before the Spanish Agency for Data Protection (AEPD). It will be ensured that they will be treated in accordance with the provisions of the Protection Law of Personal Data, exclusively for the development and good end of the study.

When personal data belonging to the Researcher and / or patients is archived or processed, The Promoter will take the appropriate measures to protect and prevent access to this data, for part of unauthorized third parties.

Any data required by the protocol may be subject to audits by the promoter, independent organizations and / or competent authorities, but the confidentiality of the data it will always be an indispensable condition.

*and. Interference with the doctor's prescription habits.*

In no case will the study interfere with the care tasks, nor will it modify the doctor's prescription habits.

*F. Pertinence of exploration by IP*

The IP is certified for the performance of Clinical Ultrasound by WINFOCUS and SEMES, SEMI, in addition to having the Certification in Echocardiography by SEMI-SEC, which justifies its aptitude to carry out this research project.

ANNEX I:

DATA COLLECTION NOTEBOOK

CRF SARCO-COVID: Measurement of Skeletal Muscle Loss  
in hospitalized patients diagnosed with COVID-19

PATIENT ID			
AGE AND SEX			
Comorbidity			
CARDIOP	PERSONAL PREVIOUS ETV		HTA / DM
MY AUNT?	OR FAMILY?	?	
NEUMOPA	IRC?		Obesity?
AUNT?	IMMUNOSUPPRESSION?		Others?
Usual treatment			
Main symptoms and time of evolution	DYSPNOEA OTHERWISE	FEVER OTHERWISE	ASTENIA / MIALGIAS OTHERWISE
DIARRHEA / NAUSEA OTHERWISE	COUGH OTHERWISE	PAIN THORACIC OTHERWISE	WEIGHT LOSS > 5% IN 3 MONTHS OTHERWISE
TA		FC	
SO2		FR	
T°		Weight (kg)	

Size (cm)  
Circumference  
waist  
Dynamometry B.  
dominant (mean of  
3)  
TBW: total body  
toilet  
FFM: fat free mass  
BCM: body cell mass

\_\_\_\_\_

Weight loss>  
Circumference  
calf

**Bioimpedanceometry**

MM: muscular  
mass  
FM: fat masS

Hb  
Creatinine  
AST  
LDH  
pO2  
pH  
D-dimer  
PCR  
Nt Pro-BNP

Leucos (Nt, L)  
Urea  
ALT  
Lactate  
pCO2  
CK  
procalcitonin  
Troponin I  
IL-6 / Ferritin

Albumin  
Total proteins  
Phosphataemia  
Folic acid  
Cholesterol

Prealbumin  
Calcemia  
Vitamin D  
B12 vitamin  
Triglycerides

**FEMORAL STRAIGHT D  
ENTRY**

Thickness      Sectional area  
maximum (mm)    (cm2)

**INTERNAL VAST D AL  
ENTRY**

Thickness      Sectional area  
maximum            (cm2)  
(mm)

**EXTERNAL VAST D AL  
ENTRY**

Thickness      Sectional area  
maximum (mm)    (cm2)

**FEMORAL STRAIGHT I TO  
HIGH**

Thickness      Sectional area  
maximum (mm)    (cm2)

**INTERNAL VAST I TO  
HIGH**

Thickness      Thickness  
maximum            maximum (mm)  
(mm)

**EXTERNAL VAST I TO  
HIGH**

Sectional area    Thickness  
(cm2)                maximum (mm)

**INTERNAL TWIN D AT INCOME**

Thickness      Sectional area      Angle of  
maximum (mm)    (cm2)                Penalty (in  
degrees)

**INTERNAL TWIN I ON ADMISSION**

Thickness      Sectional area      Angle of  
maximum (mm)    (cm2)                Penalty (in  
degrees)

**INTERNAL TWIN D ALTA**

Thickness      Sectional area      Thickness  
maximum (mm)    (cm2)                maximum  
(mm)

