#### **Four. V ARIABLES IN EVALUATION**

Data to collect:

\* PRIMARY VARIABLE:

*to. Variables related to ultrasound:*

To collect these variables, the GE VENUE will be used, the linear probe will be used (5.5–7.5 MHz) (General Electrics Healthcare, Madrid, Spain).

All patients will undergo a muscle ultrasound upon admission to the center and prior to upon discharge, using the usual muscle sweep technique. The ultrasound will be performed on the rectus femoris, vastus medialis, vastus lateralis and medial calf muscles. They will be measured:

- Muscle thickness in its cross section (in mm), in the plane of maximum thickness

in longitudinal sweep

- Cross-sectional area (in  $\text{cm}^2$ ) in the plane of maximum area in the scan longitudinal
- Angle of penetration (in degrees) of the medial twin, using the base of the angle the deep muscle fascia and as an angle the maximum inclination of the you muscle mass.

This exam will be carried out by 5 experienced physicians according to the criteria of the ACEP (American College of Emergency Physicians) and who carry out more than 10 studies ultrasounds per week and at least 3 years of experience in the performance and interpretation of ultrasound examinations. A reliability study will not be conducted given the limitation in the time and current healthcare pressure.

In addition, to avoid the possible bias that inter-operator variability would suppose in these circumstances, the research team was provided with a training program and designed internal training consisting of:

- Theoretical course on basic, systematic musculoskeletal ultrasound, medication, etc.
- Practical seminars in which an ultrasound machine and healthy models will be used to your measurement.
- Supervised practical training with real hospital patients until assessing an adequate measurement of at least 5 patients.
- The team of 5 doctors adequately trained in this technique were specific to this trial to avoid protocol deviations and any other form of interoperator variability.

\* SECONDARY VARIABLES:

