## 5. METHODOLOGY

*to. Selection of study cases*

Patients over 18 years of age who are admitted to the Hospital and whose primary diagnosis is COVID-19 pneumonia.

For this, patients who meet the criteria of inclusion. After granting verbal consent, the parameters included in the Data Collection Notebook, included in Annex I.

All examinations will be tagged with a unique code and history number Hospital clinic, and archived in digital format.

*b. Information collection:*

Once the patient has been recruited, the objectives and procedures of the study will be explained, He will provide the information sheet and you will be asked for your informed consent.

Then, according to the usual clinical practice, an evaluation will be carried out clinic that includes anamnesis, physical examination and extraction of laboratory tests, as well as other complementary tests that are considered appropriate for the patient's situation. A) Yes Also, at the time of the first assessment, a muscle ultrasound of the lower limbs, repeating it prior to discharge. All the variables collected will be collected in section 4 of this protocol.

The duration of the follow-up will be 30 days, the presence of complications in this time, by reviewing the medical history, as well as functional recovery (Barthel scale), and will be contacted by telephone, to pass a quality questionnaire of life (EuroQol-5D).

Any unexpected event that requires treatment or medical care, including mortality. Any undesirable effects will be collected observed, during hospitalization, and during follow-up for the next 30 days.

*\* The patient's CRF will include:*

Demographic variables, physical examination, laboratory findings, related to the diagnosis, treatment, as well as clinical evolution (see Annex I).

*\* Usual intervention:*

According to the usual management of COVID-19 infection, individualizing its use at the discretion of the responsible physician.

It must be taken into account that **the use of ultrasound will be carried out according to the current international recommendations (detailed below), and that strict measures will be followed to avoid contagion, it does not imply under any circumstances delay in the administration of treatment.**

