### **PROCEDURE FOR CLEANING THE MATERIAL ECOGRAPHY**

The ultrasound machine will be at all times in the consultation reserved for attention to suspected COVID.

Before carrying out: hand washing with soap and water. Will wash first with enzymatic detergent (optional) and then with alcohol 96% all the surface of the ultrasound system including cable and ultrasound support area, except for the probe. The tube will be cleaned with Clinell®.

During the procedure: the examination will be done with the “dirty” hand in contact with the patient avoiding touching the rest of the ultrasound machine to the extent the possible. The other hand (“clean”) will be left to handle the ultrasound machine (amplitude, gain, zoom, ...).

After completion: it will be washed again with 96% alcohol. Washing hands.

Wait at least until the ultrasound machine has dried after the disinfection procedure before restarting the process.

*c. Practical considerations:*

INCLUSION PHASE:

All patients admitted to HEEIZ hospital will be selected. I know will verify that they meet the inclusion criteria and none of the exclusion criteria, and they will be informed of the objectives and procedures of the study, giving them the information sheet and requesting their verbal informed consent. CRF

COMPLIANCE:

The diagnostic and therapeutic management of the patient will be carried out according to clinical practice usual, filling in the CRF all demographic variables, physical examination, diagnostic, ultrasound and follow-up variables that appear in section 4 of this protocol.

FOLLOW-UP OF PATIENTS:

Patients will be followed up to day 30 after inclusion in this study (well, after hospital discharge or until the day of death if it occurs before day 30), in order to evaluate the main variables. The follow-up will be done by reviewing the electronic medical record, and will be contacted by phone.

ANALYSIS OF RESULTS:

Once the follow-up of the last patient has been completed, the statistical analysis of the results and the final study report will be prepared.

FINANCING:

This is an unfunded study sponsored by researchers. The promoter (Group of GTEco-SEMI ultrasound) will provide the necessary material (information, notebook, methodology and logistics) to carry out the study.

*d. Schedule:*

The total duration of the project is estimated at **03 months** .

	FEBRUARY	MARCH	APRIL	APRIL
Authorization request by the CEIC and classification by AEMPS	•			
Identification of patients		•		

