**INTERNAL TWIN I ALTA**

Thickness      Sectional area      Thickness  
maximum (mm)    (cm2)                maximum (mm)

ATB                      Anti-IL 6                      Corticosteroids (days and max dose)      Corticosteroid bolus (dose and days)      Anticoagulant

O2 (modality)                      NIMV                      VM                      You go amines.                      ECMO

BARTHEL PREVIOUS ON ENTRY (date)                      WORST BARTHEL DURING ADMISSION (date)                      BARTHEL AL HIGH (date)                      BARTHEL AL MONTH OF RECLUT. (date)

SARC-F                      MUST                      FRAGILITY                      MINNESOTA

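### The printed case report form has a pennation-angle field for both medial calves at admission but none at discharge, so change in the angle cannot be computed from it

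*Combined protocol and SAP*

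**What the plan says.** Section 4 of the protocol, under the primary variable, sets out the ultrasound measurements. Thickness and cross-sectional area are taken in four muscles. A third measurement is added for the medial calf: "Angle of penetration (in degrees) of the medial twin". The context shows that this is the pennation angle. On timing, the same section says "All patients will undergo a muscle ultrasound upon admission to the center and prior to" discharge, and section 5b again plans "a muscle ultrasound of the lower limbs, repeating it prior to discharge".

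The angle is also named in a secondary objective, both in the Summary (item 10) and in section 2g. Section 5c, under Compliance, says the CRF is to be filled in with the "ultrasound and follow-up variables that appear in section 4 of this protocol".

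Annex I is the CRF. Its medial-calf blocks at admission are headed "INTERNAL TWIN D AT INCOME" and "INTERNAL TWIN I ON ADMISSION". Each has three fields: maximum thickness (mm), sectional area (cm2) and an angle in degrees. The discharge blocks are headed "INTERNAL TWIN D ALTA" and "INTERNAL TWIN I ALTA". Each also has three fields, but the third is maximum thickness (mm) again. I read D and I as right and left, and ALTA as discharge.

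**The concern.** The study is built on change between two scans. A measure recorded at admission but not at discharge gives a baseline description and nothing on loss. Section 4 places the angle under the primary variable and schedules both scans, and section 5c makes the CRF the place where the result is kept. The printed form does not carry that through for the angle.

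The analysis plan would not repair the gap: the statistical analysis part of section 5 reads as no imputation, with missing data left missing. The repeated thickness field also makes entries ambiguous. One operator may enter a second thickness and another may write the angle under the wrong label, and the database could not reliably tell the two apart.

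**Working it through.** This is a field-by-field count. The plan gives no figure of its own to reproduce.

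**Inputs.** Measurements and time points come from section 4, printed fields from the four medial-calf blocks of Annex I, and sample sizes from Summary item 11 (64) and section 3 (124).

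**Step 1: the four blocks side by side.**

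| Medial-calf block | Field 1 | Field 2 | Field 3 |
|---|---|---|---|
| Right, admission | thickness | area | angle |
| Left, admission | thickness | area | angle |
| Right, discharge | thickness | area | thickness |
| Left, discharge | thickness | area | thickness |

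**Step 2: required against printed.**

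- Required: 2 legs × 2 times × 3 measures = 12 distinct fields.
- Printed: 4 blocks × 3 = 12 fields, of which 2 repeat thickness, leaving 12 − 2 = 10 distinct fields.
- Angle fields: 2 of 2 at admission, 0 of 2 at discharge.
- Repeated thickness fields: 0 of 6 at admission, 2 of 6 at discharge.
- Legs with a paired angle: 0 of 2.

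No discharge angle field appears elsewhere in the printed form.

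**Step 3: share of the ultrasound data set.** Section 4 lists 4 muscles × 2 measures (thickness, area) + 1 angle = 9 measures per leg. The angle is 1 of the 9.

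**Step 4: upper bound on discharge angles without a labelled field.** The protocol gives two sample sizes, so there are two bounds:

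- 2 legs × 124 patients = 248
- 2 legs × 64 patients = 128

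Both assume that every patient is scanned at discharge and every form is completed exactly as printed. They are ceilings, not expected losses.

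**Step 5: could this be a fault of PDF reading?** A lost cell would leave a gap. Here each discharge block has a complete third label with its own unit, and the substitution occurs in both discharge blocks and in neither admission block. The left-leg quadriceps discharge labels, read across, run thickness, area, thickness, thickness, area, thickness. The two calf discharge blocks, read one after the other, give the same six labels in the same order. That suggests a label row copied within the form. It is an inference, because the source form cannot be seen.

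**Step 6: after correction.** With the third discharge field relabelled, angle fields rise from 2 of 4 to 4 of 4, and legs with a computable change from 0 of 2 to 2 of 2.

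**The case against.** The strongest reply is that this is a proofreading slip with little consequence:

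- **No stated analysis needs the paired angle.** The secondary objective asks only that thickness, area and angle be analysed, which admission values alone could satisfy. The main objective is loss of muscle mass, and calf thickness and area have fields at both times. The statistical section names no analysis of the angle.
- **The text already requires the discharge angle.** Section 6a binds researchers to the protocol, and five trained physicians dedicated to the study do the scans. They may well notice that the repeated label sits where the angle stood at admission.
- **Other sources may hold it.** Examinations are archived digitally (sections 3b and 5a), and section 6d mentions an e-CRF whose fields are not shown.
- **The text of Annex I is unreliable.** The neighbouring quadriceps table is visibly broken, so the calf labels may share that doubt.

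The first point stands as a limit on importance. The second and third stand as possibilities only: nothing provides a discharge angle field or plans re-measurement. Re-measurement would also need stored images that show the deep fascia and the fibre inclination, which the protocol does not guarantee. The fourth lowers confidence but does not overturn the finding, because all four calf blocks survive with complete labels. Nor is the form background text: it determines which data exist.

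**Conclusion.** The concern holds for the form as printed. The angle has a field on both legs at admission and on neither at discharge, contrary to sections 4 and 5c. Completed literally, the form gives no change in pennation angle for any patient, with a ceiling of 248 unlabelled discharge angles at 124 patients or 128 at 64.

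The damage is confined to 1 of 9 measures per leg. Calf thickness and area, which bear on the main objective, are not affected. This should be fixed, but it does not threaten the main result.

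Confidence is medium. The conclusion assumes that the calf labels in the available text match the source form and that the e-CRF, which is not shown, does not already have the missing field.

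**What to change.** Before data collection, replace the repeated thickness label with pennation angle (degrees) in both medial-calf discharge blocks, and check that the e-CRF has the same field. The cost is two labels. The section 4 examination already covers the angle, so no extra calf scan is needed.

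At the same time, check the quadriceps part of Annex I against the source form. As read, it shows the left vastus medialis at discharge with thickness twice and no area, and quadriceps blocks only for the right leg at admission and the left leg at discharge. Blocks may have been lost in reading the PDF, so this is a point to check and not a claimed error. If the source form does read this way, correct that label to area and add the missing same-leg blocks, so that change is computed within the same muscle and leg. That would add a few recorded values per scan.

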**INTERNAL TWIN I ALTA**

Thickness      Sectional area      Thickness  
maximum (mm)    (cm2)                maximum (mm)

ATB                      Anti-IL 6                      Corticosteroids (days and max dose)      Corticosteroid bolus (dose and days)      Anticoagulant

O2 (modality)                      NIMV                      VM                      You go amines.                      ECMO

BARTHEL PREVIOUS ON ENTRY (date)                      WORST BARTHEL DURING ADMISSION (date)                      BARTHEL AL HIGH (date)                      BARTHEL AL MONTH OF RECLUT. (date)

SARC-F                      MUST                      FRAGILITY                      MINNESOTA

**Loss Follow-up Mortality**

**Adverse Event (description)**

MINNESOTA REDUCED

FRIED AND WALSTSON CRITERIA

DYNAMOMETRY

*MIR / HEEIZ\_2021\_03 protocol*

*Version 2.0. February 2021*

